5.1 Efficacy assessments

5.1.1 RECIST 1.1

All imaging assessments including unscheduled visit scans should be collected on an ongoing basis and sent to an AstraZeneca (AZ) appointed Clinical Research Organisation (CRO) to enable independent central analyses.

For both Independent Central Review (ICR) and investigator review RECIST 1.1 criteria will be used to assess each patient's tumour response to treatment and allow calculation of ORR, PFS, DCR, DoR, and assess tumour shrinkage. The RECIST 1.1 guidelines for measurable, non-measurable, target and non-target lesions and the objective tumour response criteria [CR (complete response), PR (partial response), SD (stable disease) or PD (progression of disease)] are presented in [Appendix D](#). For ORR, a visit response of CR or PR must be confirmed by a later scan conducted at least 4 weeks after the initial response is observed. See [Section 4](#) for considerations related to RECIST 1.1 assessments.

The methods used at baseline for assessment of tumour burden [CT or MRI scans of chest and abdomen (including liver and adrenal glands)] must be used at each subsequent follow-up assessment. Any other areas of disease involvement should be additionally investigated based on the signs and symptoms of individual patients. CT/MRI scan of the brain should be performed in patients with known or suspected brain metastases. The baseline assessment should be performed within 28 days of treatment start. Assessments to be performed every 6 weeks relative to first dose until objective disease progression. It is important to follow the assessment schedule as closely as possible. If scans are performed outside of the scheduled visit \pm 1 week window interval and the patient has not progressed, every attempt should be

made to perform the subsequent scans at their scheduled time points. Any other sites at which new disease is suspected should also be appropriately imaged.

If the investigator is in doubt as to whether progression has occurred, particularly with response to non-target lesions (NTLs) or the appearance of a new lesion, it is advisable to continue treatment until the next scheduled assessment or sooner if clinically indicated and reassess the patient's status. If repeat scans confirm progression, then the date of the initial scan should be declared as the date of progression.

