PFS is defined as the time from enrolment until the date of objective disease progression or death (by any cause in the absence of progression) regardless of whether the patient withdraws from study therapy or receives another anti-cancer therapy prior to progression. Patients who have not progressed or died at the time of analysis will be censored at the time of the latest date of assessment from their last evaluable RECIST assessment.

However, if the patient progresses or dies after three or more missed RECIST assessments visits, the patient will be censored at the time of the latest evaluable RECIST assessment. If the patient has no evaluable visits or does not have baseline data they will be censored at 0 days unless they die within two visits of baseline.

The PFS time will always be derived based on scan/assessment dates not visit dates.

RECIST assessments/scans contributing towards a particular visit may be performed on different dates. The following rules will be applied

- Date of progression will be determined based on the earliest of the dates of the component that triggered the progression

- When censoring a patient for PFS the patient will be censored at the latest of the dates contributing to a particular overall visit assessment

Overall Survival

Overall survival is defined as the time from the date of first dose until death due to any cause. Any patient not known to have died at the time of analysis will be censored based on the last recorded date on which the patient was known to be alive.

Note: Survival calls will be made in the 2 weeks following the date of the final data cut-off for the analysis, and if patients are confirmed to be alive (if the death date is post the final data cut-off date) these patients will be censored in the analyses as of the date of the final data cut off.

HRQoL & Symptoms

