4. TUMOUR RESPONSE EVALUATION

4.1 Schedule of evaluation

CT examinations of the chest and abdomen (including liver adrenal glands) will be used to assess tumour burden at baseline and follow-up visits. CT examination with intravenous contract media administration is the preferred method. MRI should be used where CT is no feasible or it is medically contra-indicated.

Baseline tumour assessments should encompass all areas of known predilection for metastases in the disease under evaluation and should additionally investigate areas that may be involved based on signs and symptoms of individual patients and should be performed no more than 28 days before the start of study treatment. CT/MRI scan of the brain should be performed in patients with known or suspected brain metastases. Follow-up assessments should be performed every 6 weeks (± 7 days) after the start of treatment until discontinuation of study treatment or withdrawal of consent. Any other sites at which new disease is suspected should also be adequately imaged at follow-up.

If an unscheduled assessment was performed and the patient has not progressed, every attempt should be made to perform the subsequent assessments as their scheduled visits. This schedule is to be followed in order to minimise any unintentional bias caused by some patients being assessed at different frequency than other patients.

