3.6.1 Procedures for discontinuation of a subject from investigational product

Previous text:

Any subject who discontinues study treatment for reasons other than objective disease progression should have tumour assessments performed as scheduled in the protocol (See Table 1) until objective disease progression is documented or death occurs, unless consent is withdrawn. Study procedures related to PROs, SAEs and anti-cancer treatment must be captured until the subject no longer has RECIST 1.1 assessments (disease progression or permanent withdrawal from the study).

Revised text:

Any subject who discontinues study treatment for reasons other than objective disease progression should have tumour assessments performed as scheduled in the protocol (See Table 1) until objective disease progression is documented or death occurs, unless consent is withdrawn. ~~Study procedures related to PROs, SAEs and anti-cancer treatment must be captured until the subject no longer has RECIST 1.1 assessments (disease progression or permanent withdrawal from the study).~~ **Refer to Section 4.3 for further details.**

Section of protocol affected:

Table 1 Study Plan

Previous text:

Footnote r Following AZD9291 discontinuation, SAEs considered related to study procedures should continue to be collected until disease progression.

Revised text:

Footnote r Following AZD9291 discontinuation, SAEs considered related to study procedures should continue to be collected **as outlined in Table 8.**

Time relative to dose	Screening (baseline)	Cycle 1 Day 1	Cycle 2 Day 1	Cycle 3 Day 1
24 hours (±1 hour)	X			X (D2, pre-dose)

1 Since there is no dosing at Screening, ECG recordings should start at a time that would be consistent with planned dosing times at Cycle 1 Day 1, Cycle 2 Day 1 and Cycle 3 Day 1 (for baseline purposes).

Revised text:

Time relative to dose	Screening (baseline)	Cycle 1 Day 1	Cycle 2 Day 1	Cycle 3 Day 1
Pre-dose (-10 to 0 min) ²	X ¹	X	X	X
1 hour (±5 min)	X	X		X
2 hours (±10 min)	X	X		X
4 hours (±10 min)	X	X		X
6 hours (±10 min)	X	X		X
8 hours (±10 min)	X	X		X
10 hours (±10 min)	X			X
12 hours (±1 hour)	X			X
24 hours (±1 hour)	X			X (D2, pre-dose)

1 Since there is no dosing at Screening, ECG recordings should start at a time that would be consistent with planned dosing times at Cycle 1 Day 1, Cycle 2 Day 1 and Cycle 3 Day 1 (for baseline purposes).

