8.4 Outcome measures for analyses

Previous text:

Progression Free Survival (PFS)

PFS is defined as the time from enrolment until the date of objective disease progression or death (by any cause in the absence of progression) regardless of whether the patient withdraws from study therapy or receives another anti-cancer therapy prior to progression. Patients who have not progressed or died at the time of analysis will be censored at the time of the latest date of assessment from their last evaluable RECIST assessment.

Revised text:

Progression Free Survival (PFS)

PFS is defined as the time from **date of first dose** until the date of objective disease progression or death (by any cause in the absence of progression) regardless of whether the patient withdraws from study therapy or receives another anti-cancer therapy prior to

progression. Patients who have not progressed or died at the time of analysis will be censored at the time of the latest date of assessment from their last evaluable RECIST assessment.

Section of protocol affected:

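### The PFS censoring rules in 8.4 use two unaligned tolerances, so deaths at about weeks 12 to 18 in patients with no evaluable scan are removed at day 0, although a death after an equal gap following an evaluable scan counts

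*Supplement*

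**What the plan says.** All of the rules are in protocol section 8.4, under Progression Free Survival.

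- **Time origin, as revised by Amendment 2:** "PFS is defined as the time from date of first dose until the date of objective disease progression", or death from any cause.
- **Missed-visit rule:** "if the patient progresses or dies after three or more missed RECIST assessments visits, the patient will be censored" at the latest evaluable assessment. A death after exactly two missed visits is therefore an event.
- **Rule for patients never evaluated:** for those with no evaluable visit or no baseline data, "they will be censored at 0 days unless they die within two visits of baseline".

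The schedule comes from section 5.1.1 ("Assessments to be performed every 6 weeks relative to first dose until objective disease progression") and Appendix D section 4.1 ("Follow-up assessments should be performed every 6 weeks (± 7 days) after the start of treatment"). Amendment 2 changes the starting point of PFS but neither tolerance. Section 8.9.5 plans one sensitivity analysis of PFS, on investigator data with the same methods, so it inherits both rules. No separate analysis plan is shown.

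**The concern.** The two sentences stand next to each other and deal with the same problem: how long a gap in assessment may be before a death is no longer accepted as a PFS event. One accepts a death until three visits have been missed. The other stops at two visits from baseline. No reason is given for the difference. Elsewhere in 8.4, time to symptom deterioration uses one tolerance throughout: a death counts within two visits, and censoring follows two or more missed assessments. The mismatch for PFS therefore looks unintended.

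At stake are known deaths that leave the PFS risk set at day 0. A patient who dies some three to four months after first dose without an evaluable scan is unlikely to be typical of those who remain, so the censoring is probably informative. There is no control arm in which the effect could offset, and 8.9.2 reports PFS at 6, 12 and 18 months, all later than the deaths in question.

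**Working it through.** No power or precision figure in the protocol depends on these rules, so there is no stated figure to reproduce. The check sets the rules side by side on the calendar and then sizes the effect.

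**Inputs.** Scans every 6 weeks from first dose (5.1.1), so weeks 6, 12, 18 and 24 are days 42, 84, 126 and 168. Window ±7 days (Appendix D 4.1). About 175 patients (8.2). I read visits in both rules as scheduled RECIST visits.

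**Step 1: the limits in days.**

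- Two visits from baseline: day 84, or 84 + 7 = day 91 with the window.
- Third visit missed: day 126, or 126 + 7 = day 133.

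| Death, in days from the last evaluable scan (from first dose if none) | Never evaluated | Earlier evaluable scan |
|---|---|---|
| Up to 84 (91 with window) | event | event |
| 85 to 126 (92 to 133) | censored at day 0 | event |
| After 126 (133) | censored at day 0 | censored at that scan |

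The rules disagree on event status only in the middle row.

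**Step 2: a matched pair.**

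- Patient A has no evaluable scan and dies on day 100, having missed weeks 6 and 12. Result: censored at day 0.
- Patient B has an evaluable scan at week 6 (day 42), misses weeks 12 and 18, and dies on day 42 + 100 = 142, before week 24 (day 168). Result: event at day 142.

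Each missed two visits and had a 100-day gap.

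**Step 3: how much of the early mortality is lost.** Assume exponential survival in such patients. The share of deaths in the first 18 weeks that fall in the first 12, and so stay events, is (1 − S(12)) / (1 − S(18)). It is 81% for a median of 2 months and 69% for 16 months. Section 1.4 gives about 10 and 16 months as background medians; shorter ones are assumed. The other 19% to 31% fall in the affected band.

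**Step 4: effect on 6-month PFS.** Let m be the number of never-evaluated patients who die in the band (placed at week 15). Assume the other 175 − m have exponential PFS S(t) with median 6 or 9 months, and no other censoring before 6 months.

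- m censored at day 0: estimate = S(6).
- m counted as events: estimate = S(6) × (175 − m)/175.
- Difference = S(6) × m/175.

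| m | Median 6 months, S(6) = 50.0% | Median 9 months, S(6) = 63.0% |
|---|---|---|
| 1 | 0.3 points | 0.4 points |
| 3 | 0.9 points | 1.1 points |
| 5 | 1.4 points | 1.8 points |

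The median would fall from 6 to 5.95 months (m = 1) or 5.75 (m = 5), and from 9 to 8.93 or 8.62. A cruder calculation agrees. With 70 true events of 175 by 6 months (PFS 60%), dropping k of them at day 0 gives 105/(175 − k): 105/173 = 60.7% for k = 2 and 105/170 = 61.8% for k = 5.

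**Step 5: direction before those deaths.** Suppose 30 other events by day 84 and no other censoring. With five such patients kept, PFS is 145/175 = 82.9%. With them dropped at day 0, it is 140/170 = 82.4%. The shift is upward only once the deaths have occurred.

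**The case against.** The strongest reply is that the rules are not contradictory. The first censors at the last evaluable scan and so presupposes one; the second is a specific rule for patients who have none, and a sponsor may choose a tighter limit there. The affected group is also narrow: no evaluable scan at all, including unscheduled ones, followed by death in a window of about six weeks. At 60% with n = 175, the 95% half-width is 1.96 × √(0.6 × 0.4/175) = 7.3 points, well above any effect shown here. Windows in days and censoring sensitivity analyses could sit in an analysis plan that is not shown.

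Much of this stands. The effect is small, PFS is secondary and descriptive, and n = 175 is only approximate for PFS by independent review, which uses the evaluable-for-response set (8.3.2). What does not follow is that the limits should differ. The protocol itself states both and explains neither.

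A reader might infer more than the documents support:

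- **That the worst early outcomes are removed.** They are not. The exception keeps deaths to about week 12 or 13; the next band is lost.
- **That stopping treatment early triggers the rule.** It does not. The trigger is having no evaluable visit or no baseline data, and 3.6.1 as amended says "Any subject who discontinues study treatment for reasons other than objective disease progression should have tumour assessments performed as scheduled in the protocol". Patients without an evaluable scan can still arise. Scans may all be read as not evaluable. Section 6.7 withdraws some patients from the study, which 3.7 defines as ending assessments too. Appendix D 4.1 ends scans at treatment discontinuation, which must be reconciled with 3.6.1.
- **That PFS is always raised.** Step 5 shows a slight lowering before the affected deaths.

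**Conclusion.** The point holds as an inconsistency with a modest bias. Read as written, 8.4 removes at day 0 the never-evaluated patients who die at about weeks 12 to 18 (13 to 19 with the window), while a death after an equal gap following an evaluable scan is an event. PFS after those deaths is raised, including the reported 6-, 12- and 18-month estimates. At 6 months the rise is about 0.3 to 1.8 points for 1 to 5 such patients of 175. That range rests on an assumed number of patients, assumed exponential PFS with a median of 6 or 9 months, and no other early censoring. The documents give no count.

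The primary endpoint is untouched: a patient with measurable baseline disease and no evaluable scan stays in the ORR denominator as a non-responder. OS counts every death. The reason to act is that the planned sensitivity analysis cannot reveal the effect and the correction is very cheap, not that the bias is large.

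**What to change.** Change the second rule in 8.4 so that both limits are three scheduled RECIST visits. Suggested sense: a patient with no evaluable visit or no baseline data is censored at day 0, except that a death within three scheduled RECIST visits of baseline, meaning on or before day 133 from first dose (week 18 plus the 7-day window), is a PFS event at the date of death. Apply it to PFS by independent review and by investigator.

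The limit should be a time from first dose, not a count of missed visits. A patient who attended every scan but had all of them read as not evaluable has missed none. Under a missed-visit limit, that patient's death even a year later would become an event. Stating the day also removes doubt about which visits are meant, since clinic visits in the early cycles are more frequent than scans.

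The cost is one sentence, a change to the derivation program, and a PFS that may be slightly less favourable.

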i To be taken at the same time as the screening biopsy is taken or prior to mutation screening. All plasma samples are required by AstraZeneca, regardless of the outcome of the mutation screening.

j Collect every 6 weeks up to and including progression (corresponding with the RECIST assessments – and continuing after treatment discontinuation in absence of disease progression).

k If for any reason the sample is not drawn prior to first dose it may be taken at any visit until the last study visit.

l To be obtained at one time point at any time from Cycle 2 Day 1 onwards

m At least one lesion, not previously irradiated and not chosen for biopsy during the study screening period, that can be accurately measured.

- n Assess every 6 weeks relative to first dose until end of study (including survival follow-up period) and at the time of progression.
- o Assess every 3 weeks relative to first dose until end of study (including survival follow-up period) and at the time of progression.
- p PRO-CTCAE will only be administered in those countries where a linguistically validated version exists.
- q Assessed at Cycle 7 Day 1 then every 3 weeks relative to first dose thereafter until end of study (including survival follow-up period) and at the time of progression.
- r Following AZD9291 discontinuation, SAEs considered related to study procedures should continue to be collected until disease progression.
- s Survival status including anti-cancer treatment to be performed every 6 weeks (relative to first dose) following disease progression or withdrawal from treatment.
- t Record subsequent response/progression data every 6 weeks until first confirmed disease progression on a subsequent treatment.

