4.3.4 Survival follow-up

Assessments for survival should be made every 6 weeks (relative to first dose) following objective disease progression or withdrawn from treatment. Survival information may be obtained via telephone contact with the patient, patient's family or by contact with the patient's current physician. In addition to the survival status, the following assessments are also required post progression as detailed in the study plan (see [Table 1](#)):

- EORTC QLQ-C30 and EQ-5D-5L every 6 weeks.
- EORTC QLQ LC13 and PRO-CTCAE every 3 weeks.
- Anti-cancer therapy collected every 6 weeks.
- Subsequent response/progression data every 6 weeks until the first confirmed disease progression on a subsequent treatment.

Survival data will be collected up to the time of the final OS analysis. Patients should be contacted in the week following the data cut-off for the final survival analyses to provide complete survival data.

The status of ongoing, withdrawn (from the study) and “lost to follow-up” patients at the time of an overall survival analysis should be obtained by the site personnel by checking the patients notes, hospital records, contacting the patients general practitioner and checking publicly available death registries. In the event that the patient has actively withdrawn consent to the processing of their personal data, the vital status of the patient can be obtained by site personnel from publicly available resources where it is possible to do so under applicable local laws.

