ORR rate is defined as the number (%) of subjects with measurable disease with at least one visit response of CR or PR that is confirmed at least 4 weeks later (according to ICR for the primary analysis). Data obtained up until progression, or last evaluable assessment in the absence of progression, will be included in the assessment of RR. However, any complete response or partial response which occurred after a further anticancer therapy was received will not be included in numerator of the ORR calculation.

In the case where a subject has two non-consecutive visit responses of PR, then, as long as the time between the 2 visits of PR is greater than 4 weeks and there is no PD between the PR visits, the subject will be defined as a responder. Similarly, if a subject has visit responses of CR, NE, CR, then, as long as the time between the 2 visits of CR is greater than 4 weeks, then a best response of CR will be assigned.

Duration of Response (DoR)

Duration of response will be defined as the time from the date of first documented response, (that is subsequently confirmed) until date of documented progression or death in the absence of disease progression, the end of response should coincide with the date of progression or death from any cause used for the PFS endpoint. The time of the initial response will be defined as the latest of the dates contributing towards the first visit response of PR or CR. If the response is not confirmed, it will not be included.

If a subject does not progress following a response, then their duration of response will use the PFS censoring time.

Disease control rate (DCR)

Disease control rate is defined as the percentage of patients who have a BoR of CR or PR or SD.

Tumour Shrinkage

Tumour shrinkage will be assessed using RECIST tumour response. The absolute change and percentage change from baseline in sum of tumour size at each assessment will be calculated. The best change in tumour size will include all assessments prior to progression or start of subsequent anti-cancer therapy.

Progression Free Survival (PFS)

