Table 10 Visit Response for HRQoL and disease-related symptoms

Score	Change from baseline	Visit Response
LC13 symptom scales/items	$\geq +5$	Worsened
	≤ -5	Improved
	Otherwise	Stable
C30 symptom scales/items	$\geq +10$	Worsened
	≤ -10	Improved
	Otherwise	Stable
C30 functional scales and Global health status	$\geq +10$	Improved
	≤ -10	Worsened
	Otherwise	Stable

Time to symptom deterioration

For each of the symptoms scales/items in QLQ LC13, time to symptom deterioration will be defined as the time from enrolment until the date of first clinically meaningful symptom deterioration (an increase in the score from baseline of ≥ 5) or death (by any cause) in the absence of a clinically meaningful symptom deterioration, regardless of whether the patient withdraws from study therapy or receives another anticancer therapy prior to symptom deterioration. Death will be included as an event only if the death occurs within two visits of the last PRO assessment where the symptom change could be evaluated.

Patients whose symptoms (as measured by QLQ LC13) have not shown a clinically meaningful deterioration and who are alive at the time of the analysis will be censored at the time of their last PRO assessment where the symptom could be evaluated. Also, if symptoms progress after two or more missed PRO assessments or the patient dies after two or more missed PRO assessments, the patient will be censored at the time of the last PRO assessment where the symptom could be evaluated. If a patient has no evaluable assessments or does not have baseline data they will be censored at day 1. The population for analysis of time to symptom deterioration will include a subset of the FAS population who have baseline scores ≤ 95 .

Symptom Improvement Rate

The symptom improvement rate will be defined as the number (%) of patients with two assessments at least 18 days apart (i.e. 21 days allowing a visit window of 3 days) which showed a clinically meaningful improvement (a decrease from baseline score >5 for LC13 scales/items or >10 for C30 scales/items) in that symptom from baseline. The denominator will consist of a subset of the FAS population who have a baseline symptom score ≥ 5 (LC13 scales/items) or ≥ 10 (C30 scales/items).

Time from enrolment to second progression (PFS2) (exploratory)

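### The symptom improvement rate counts any two improved questionnaires at least 18 days apart, with no cut at subsequent anticancer therapy and no consecutiveness rule, so it can overstate improvement on AZD9291

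*Supplement*

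**What the plan says.** Protocol Section 8.4 (Symptom Improvement Rate) defines the numerator: "The symptom improvement rate will be defined as the number (%) of patients with two assessments at least 18 days apart". The gap is a three-week interval less a 3-day tolerance. Both assessments must pass the improvement threshold, namely "a decrease from baseline score >5 for LC13 scales/items or >10 for C30 scales/items". On the denominator it says: "The denominator will consist of a subset of the FAS population who have a baseline symptom score" at or above 5 (LC13) or 10 (C30). Nothing there requires the two assessments to be consecutive, rules out worsening between them, closes the window, or deals with progression or subsequent therapy. Neither amendment alters the paragraph.

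Collection of both questionnaires runs well past study treatment. The Table 1 footnotes read, for LC13, "Assess every 3 weeks relative to first dose until end of study (including survival follow-up period) and at the time of progression", and for C30, "Assess every 6 weeks relative to first dose until end of study (including survival follow-up period) and at the time of progression". Section 4.3.4 repeats the post-progression schedule ("EORTC QLQ LC13 and PRO-CTCAE every 3 weeks", with C30 every 6 weeks).

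Elsewhere in Section 8.4 the plan takes a position on later therapy. For ORR, "any complete response or partial response which occurred after a further anticancer therapy was received will not be included in numerator of the ORR calculation". Best change in tumour size is cut at progression or subsequent therapy. Time to symptom deterioration, as amended, states that switching therapy is ignored. For the improvement rate the plan is silent.

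**The concern.** Section 8.4 names LC13 lung-cancer symptoms as the primary patient-reported outcome measures, and the related objective is the effect of AZD9291 on symptoms. Section 8.9.2 gives each LC13 improvement rate a 95% confidence interval. The study has one arm, so no comparator offsets improvement under a later drug or form-to-form fluctuation, and the interval reflects neither.

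Two kinds of patient could be counted as improved without sustained improvement on AZD9291. One has at least one of the two qualifying forms after starting the next anticancer therapy. The other has two isolated good forms, perhaps months apart, with stable or worse forms in between. The threshold filters out little of this. LC13 items have four categories scored 0 to 100, so one category is 100/3, about 33 points, on a single item, and about 33/3 = 11 points on the three-item dyspnoea scale. Both exceed 5.

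**Working it through.** **The plan's own figure.** The minimum gap is 21 − 3 = 18 days, as stated. The plan gives no expected improvement rate.

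**Direction (no assumptions needed).**
- Any two qualifying forms before subsequent therapy are also two qualifying forms over all follow-up.
- Any unbroken run of improved forms spanning 18 days contains two improved forms 18 days apart.
- The denominator depends only on the baseline score.
- Hence the rate as written is at least as high as the restricted rate. Patients who stop completing forms early count as not improved under both rules.
- The reports fall about 3 months, about 8 months and 12–24 months after the last enrolment (Sections 8.1 and 8.9.4, as amended). Enrolment is complete by then, so the patient set is the same and the rate can only stay or rise from one report to the next.

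**Size of the later-therapy part (all inputs assumed).** Let r0 be the rate using only forms before subsequent therapy. Let s be the share of the remaining patients who start another therapy and still complete forms. Let q be the chance that such a patient then qualifies.

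Rate as written = r0 + (1 − r0) × s × q

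| r0 | s | q | Excess | Rate as written |
|---|---|---|---|---|
| 50% | 10% | 10% | 0.50 × 0.10 × 0.10 = 0.5 points | 50.5% |
| 40% | 10% | 10% | 0.60 × 0.10 × 0.10 = 0.6 points | 40.6% |
| 40% | 50% | 30% | 0.60 × 0.50 × 0.30 = 9.0 points | 49.0% |
| 30% | 50% | 30% | 0.70 × 0.50 × 0.30 = 10.5 points | 40.5% |

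Over r0 = 30–50%, s = 10–50% and q = 10–30%, the excess is 0.5 to 10.5 points. It is zero if s or q is zero.

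**Illustration of the open window.** Assume no true change, independent forms and a fixed chance p per form of looking improved. LC13 is taken weekly for 6 weeks and then every 3 weeks; the week of the switch is an assumption. C30 is taken every 6 weeks. With n forms, any two C30 forms are far enough apart, so

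P(C30) = 1 − (1−p)^n − np(1−p)^(n−1)

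For LC13, subtract also the 9 pairs and 4 triples of weekly forms that lie within 14 days:

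P(LC13) = P(C30 formula) − 9p²(1−p)^(n−2) − 4p³(1−p)^(n−3)

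| By week | LC13 forms | p = 10% | p = 5% | C30 forms | p = 10% | p = 5% |
|---|---|---|---|---|---|---|
| 12 | 8 | 14% | 4% | 2 | 1% | 0.2% |
| 35 | 15 | 43% | 16% | 5 | 8% | 2% |
| 52 | 21 | 62% | 27% | 8 | 19% | 6% |

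Real scores are correlated over time. Simulating LC13 with p = 10%, correlation 0 to 0.5 between adjacent forms and a weekly phase of 3 to 6 weeks gives 33–43% at week 35 under the plan's rule. Requiring every form across an 18-day span to be improved gives 8–21%. At correlation 0.8 the figures are 27–29% against about 22%. The gap depends heavily on inputs the documents do not supply.

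**The case against.** **The SAP is not among the documents and could set the window.** Section 8.1 promises one. This stands as a caveat: inclusion of forms after a change of therapy follows from a literal reading, not from an explicit statement. But Section 8.4 states this definition in full, whereas further detail for PK, safety and PRO-CTCAE is expressly left to the SAP.

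**The plan's other symptom endpoint ignores later therapy on purpose.** That is correct for time to deterioration, so an any-time approach is not foreign to this plan. There the choice is written down; here it is not. The ORR rule also accepts non-consecutive partial responses, provided no progression lies between them. The proposed rule is stricter than that, and this part is a matter of judgement.

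**The endpoint is descriptive.** There is no test or success threshold. Section 8.9.2 also reports improved, stable and worsened proportions and mean change at each time point, so the rate does not stand alone. This limits the consequence.

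**Stronger readings a reader might infer.**
- *The rate does overstate benefit.* The documents support only that it can, and that it cannot be lower than the restricted rate.
- *A third to three-fifths of patients would be falsely counted.* Those figures come from an assumed 10% per-form chance, concern LC13 only, and shrink for C30, for smaller chances and for higher correlation.
- *Later therapy adds about 6 points.* Taking the 20–30% platinum response rate in Section 1.1, with half of patients switching and half of those not already improved, gives 0.50 × 0.25 × 0.50 = 6.25 points. That response rate is for platinum-naive patients. About 125 of the 175 have already had a platinum doublet, and Section 1.1 cites generally under 10% for that setting. Reweighting gives (50 × 25% + 125 × 10%)/175 = 14.3%, and 0.50 × 0.143 × 0.50 = 3.6 points. Even this uses tumour response in place of symptom improvement, and both halves are unsourced.
- *Everything after progression is misattributed.* Sections 1.5 and 4.2 allow AZD9291 beyond RECIST progression, so a post-progression form may still be an on-drug form.

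**Conclusion.** The concern holds as a loose definition. Taken literally, Section 8.4 allows improvement under a later anticancer therapy, and isolated non-adjacent improvements, to count towards the symptom improvement rate. The direction is certain from the wording alone: the rate is never below one restricted to sustained improvement before subsequent therapy, and it can only stay or rise at later data cuts. The size is not known. The 0.5 to 10.5 points for later therapy and the open-window percentages are illustrations under assumed inputs; the true excess could be nil. It is worth correcting because the study has no control arm and LC13 symptoms are its leading patient-reported measures. The primary ORR analysis is not affected.

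**What to change.** In Section 8.4 and the SAP, count a patient as improved on a symptom only if a clinically meaningful decrease from baseline is present at consecutive evaluable assessments, the first and last at least 18 days apart, all before the start of subsequent anticancer therapy. While LC13 is weekly, this means an unbroken run of improved forms, since two adjacent weekly forms do not span 18 days.

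Do not make RECIST progression the main cut; that would discard improvement in patients still taking AZD9291. A version cut at progression and the current any-time rate can be supplementary. If the any-time rate is what the sponsor intends, say so, as is done for time to symptom deterioration.

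The cost is one sentence and a programming rule. No new data are needed, because subsequent anticancer therapy is already recorded (Sections 4.3.3, 4.3.4 and 5.8). The drawbacks are a somewhat lower reported rate and the loss of some patients whose improvement is real but intermittent. Any simulated magnitude quoted in support should be labelled as an illustration under assumed inputs.
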